## Acceptable hormonal methods:

- Etonogestrel implants (eg, Implanon®, Norplant®) PLUS male condom
- Normal and low dose combined oral pills PLUS male condom
- Hormonal shot or injection (eg, Depo-Provera) PLUS male condom
- Intrauterine system device (eg, levonorgestrel-releasing intrauterine system Mirena®) PLUS male condom
- 14. As determined by the enrolling physician or protocol designee, ability of the subject to understand and comply with study procedures for the entire length of the study
- 15. All subjects must have adequate archival tissue available prior to registration (i.e., at least 15 unstained slides or paraffin block). Archival tissue should represent invasive or metastatic urothelial cancer with a preference for metastatic tissue if available. Archival tissue should be identified at screening and shipped by C1D1. Subjects without adequate tissue may be considered on a case by case basis after discussion with the sponsor-investigator.

## 3.2 Exclusion Criteria

Subjects meeting any of the criteria below may not participate in the study:

- 1. Active infection requiring systemic therapy.
- 2. Pregnant or breastfeeding (**NOTE:** breast milk cannot be stored for future use while the mother is being treated on study).
- 3. Known additional malignancy that is active and/or progressive requiring treatment; subjects with other malignancies that have been definitively treated and who have been rendered disease free will be eligible.
- 4. Prior treatment with a PARP inhibitor, including olaparib.
- 5. Treatment with any investigational drug within 30 days prior to registration.

Version Date: 15MAY2019 Confidential Page 27 of 60

- 6. Involvement in the planning and/or conduct of the study (applies to both AstraZeneca staff and/or staff at the study site).
- 7. Resting ECG with QTc > 470 msec on 2 or more time points within a 24 hour period or family history of long QT syndrome.
- 8. Concomitant use of known strong CYP3A inhibitors (eg. itraconazole, telithromycin, clarithromycin, protease inhibitors boosted with ritonavir or cobicistat, indinavir, saquinavir, nelfinavir, boceprevir, telaprevir) or moderate CYP3A inhibitors (eg. ciprofloxacin, erythromycin, diltiazem, fluconazole, verapamil). The required washout period prior to starting olaparib is 2 weeks.
- 9. Concomitant use of known strong (eg. phenobarbital, enzalutamide, phenytoin, rifampicin, rifabutin, rifapentine, carbamazepine, nevirapine and St John's Wort) or moderate CYP3A inducers (eg. bosentan, efavirenz, modafinil). The required washout period prior to starting olaparib is 5 weeks for enzalutamide or phenobarbital and 3 weeks for other agents.
- 10. Subjects with myelodysplastic syndrome/acute myeloid leukemia or with features suggestive of MDS/AML.
- 11. Major surgery within 2 weeks of starting study treatment and subjects must have recovered from any effects of any major surgery.
- 12. Subjects considered a poor medical risk due to a serious, uncontrolled medical disorder, non-malignant systemic disease or active, uncontrolled infection. Examples include, but are not limited to, uncontrolled ventricular arrhythmia, recent (within 3 months) myocardial infarction, uncontrolled major seizure disorder, unstable spinal cord compression, superior vena cava syndrome, extensive interstitial bilateral lung disease on High Resolution Computed Tomography (HRCT) scan, history of pneumonitis, or any psychiatric disorder that prohibits obtaining informed consent.
- 13. Subjects unable to swallow orally administered medication and subjects with gastrointestinal disorders likely to interfere with absorption of the study medication.
- 14. Immunocompromised subjects, e.g., subjects who are known to be serologically positive for human immunodeficiency virus (HIV).
- 15. Subjects with a known hypersensitivity to olaparib or any of the excipients of the product.
- 16. Subjects with known active hepatitis (i.e. Hepatitis B or C) due to risk of transmitting the infection through blood or other body fluids.
- 17. Previous allogeneic bone marrow transplant or double umbilical cord blood transplantation (dUCBT).

Version Date: 15MAY2019 Confidential Page 28 of 60

#### 4. SUBJECT REGISTRATION

All subjects must be registered through HCRN's electronic data capture (EDC) system. Subjects will be considered registered when an "on study" date is entered into the EDC system.

Subjects must be registered prior to starting protocol therapy and begin study treatment within 7 business days of registration.

#### 5. TREATMENT PLAN

This is a single-arm open label phase II trial of olaparib in subjects with DDR mutant metastatic urothelial cancer. Subjects will receive olaparib, in the absence of prohibitive adverse events, until the time of disease progression.

# 5.1 Olaparib

Olaparib tablets will be packed in high-density polyethylene (HDPE) bottles with child-resistant closures. Each dosing container will contain sufficient medication for at least 28 days plus overage. Olaparib will be dispensed to subjects on Day 1 of each cycle thereafter until the patient completes the study, withdraws from the study or closure of the study.

Study treatment is available as a film-coated tablet containing 150 mg or 100 mg of olaparib. Subjects will be administered olaparib orally twice daily. Olaparib tablets should be taken at the same time each day, approximately 12 hours apart. The starting dose of olaparib tablets will be dependent on the subject's calculated creatinine clearance (CrCl). Subjects with a CrCl of  $\geq$  40 mL/min will start at a dose of olaparib tablets of 300 mg twice a day (total 600 mg per day). Subjects with a CrCl of  $\geq$  30 to  $\leq$  40 mL/min will start at a dose of olaparib tablets 200 mg twice a day (total 400 mg per day).

Olaparib should be taken with one glass of water. The tablets should be swallowed whole and not chewed, crushed, dissolved, or divided. Olaparib tablets can be taken with or without food. It is not recommended to consume grapefruit juice or consume Seville oranges while on olaparib therapy.

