#### **Correlative Studies**

Archival tumor tissue at registration

Tissue at progression if subject undergoing standard of care biopsy Peripheral blood pre-dose C1D1, C3D1, C5D1, and at progression and/or end of treatment

Continue olaparib until disease progression, toxicity, or patient or site investigator choice

\*The starting dose of olaparib will be 300 mg PO BID. Subjects with a calculated creatinine clearance of > 30 to < 40 mL/min will start at a dose of olaparib tablets 200 mg twice a day.

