# 6.3.3 Renal Impairment

If subsequent to study entry and while still on study therapy, a patient's estimated CrCl falls below the threshold for study inclusion, retesting should be performed promptly.

Version Date: 15MAY2019 Confidential Page 35 of 60

A dose reduction is recommended for subjects who develop a decline in renal function as defined by a calculated creatinine clearance by Cockcroft-Gault equation of between 31 and 39 ml/min for any reason during the course of the study: the dose of olaparib should be reduced to 200mg BID.

Olaparib should be discontinued if the calculated creatinine clearance declines to  $\leq 30$  ml/min.

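### As extracted, Section 5.1 gives two starting doses at a creatinine clearance of exactly 40 mL/min, its lower bound disagrees with three other places, and 6.3.3 leaves gaps if clearance keeps its decimals

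*Combined protocol and SAP*

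**What the plan says.** Creatinine clearance (CrCl), calculated by Cockcroft-Gault, governs dose in four places in the protocol.

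- **Section 5.1 (starting dose).** The upper band is CrCl ≥ "40 mL/min will start at a dose of olaparib tablets of 300 mg twice a day (total 600 mg per day"). The lower band, as extracted, is ≥ 30 to ≤ 40 "mL/min will start at a dose of olaparib tablets 200 mg twice a day (total 400 mg per day").
- **Schema footnote (starting dose).** The default is stated first: "The starting dose of olaparib will be 300 mg PO BID". The exception is "Subjects with a calculated creatinine clearance of > 30 to < 40 mL/min will start at a dose" of 200 mg twice a day.
- **Inclusion criterion 11 (Synopsis and Section 3.1).** CrCl must be above 30 mL/min, so 30 is excluded. A note in Section 3.1 refers to the SPM for the calculation.
- **Section 6.3.3 (on study).** A reduction to 200 mg twice daily is recommended for a calculated clearance "of between 31 and 39 ml/min for any reason during the course of the study". Then: "Olaparib should be discontinued if the calculated creatinine clearance declines to" 30 ml/min or lower. Prompt retesting is asked for when clearance falls below the inclusion threshold.

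Section 6.1 and Table 1 in 6.1.1 give a 300 mg starter two reduction steps (250 mg, then 200 mg, twice daily). Section 6.1 gives subjects who start at 200 mg none.

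**The concern.** A dosing rule based on a measured quantity should give one instruction for each value the quantity can take, and the same instruction wherever it is printed. Here the two starting-dose statements use different signs at both ends of the lower band. One of them overlaps the upper band at 40. The on-study rule uses whole-number limits for a calculated quantity, and the protocol states no rounding convention.

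Subjects near these limits are foreseeable. Criterion 9 makes a clearance above 30 but below 60 one route to entry. The metabolic panel, which includes creatinine, is scheduled at each cycle. Section 1.5.4 lists raised creatinine as a common reaction and reports it in 44% of olaparib subjects against 29% on placebo in the ovarian cancer trial tabulated there.

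At stake are consistent dosing between sites and the safety of subjects with reduced renal function. The primary analysis and the sample size are not affected.

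**Working it through.** The plan gives no figure to reproduce here. The check applies each rule, as extracted, to values around its limits.

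| CrCl (mL/min) | Eligible (> 30) | 5.1 starting dose, mg twice daily | Schema starting dose, mg twice daily | 6.3.3 on study |
|---|---|---|---|---|
| 30 | no | 200 | outside the 200 mg band | stop |
| 30.5 | yes | 200 | 200 | no instruction |
| 31 | yes | 200 | 200 | reduce to 200 |
| 39 | yes | 200 | 200 | reduce to 200 |
| 39.5 | yes | 200 | 200 | no instruction |
| 40 | yes | 300 and 200 | 300 | above the reduction band |
| 40.1 | yes | 300 | 300 | above the reduction band |

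**Starting dose.** On a 0.1 mL/min grid, the only eligible value with two doses under 5.1 is 40.0. No eligible value lacks a dose under either 5.1 or the Schema.

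**Value of 30.** Section 5.1 includes it. The Schema band and criterion 11 exclude it, and 6.3.3 stops drug there. Because criterion 11 excludes it, no one can enter at 30. It could matter only if clearance were recalculated between screening and the first dose.

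**On-study gaps in 6.3.3, decimals kept.**
- Width with no instruction: (31 − 30) + (40 − 39) = 2 of the 10 mL/min between 30 and 40.
- On the 0.1 grid from 30.1 to 39.9 there are 99 values. Those with no instruction are 30.1 to 30.9 (9) and 39.1 to 39.9 (9), so 18 of 99.
- A value of 30.5 does not trigger the retest clause, because it is still above 30.

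**Whole numbers instead.** Section 6.3.3 becomes contiguous: ≤ 30 stop, 31 to 39 reduce, 40 and above no renal action. The 5.1 overlap then covers every subject whose value rounds to 40. With rounding to the nearest whole number, that is an unrounded 39.5 up to 40.5.

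**What remains under each combination:**

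| 5.1 signs in the source PDF | CrCl with decimals | CrCl in whole numbers |
|---|---|---|
| As extracted | Overlap at exactly 40; 30 included; gaps in 6.3.3 | Overlap for all rounded to 40; 30 included; no gaps |
| Same as the Schema | Gaps in 6.3.3 only | No conflict; convention still unstated in the protocol |

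**The case against.** The best reply has three parts.

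First, the overlap at 40 and the inclusion of 30 both rest on inequality signs in a converted PDF. The same criterion 11 platelet limit appears as > 100 in the Synopsis and ≥ 100 in Section 3.1, so the text alone cannot show whether such differences are the sponsor's or the conversion's. This stands: if the PDF of 5.1 reads like the Schema, both points go. The gaps in 6.3.3 do not depend on those signs.

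Second, the limits of 31 and 39 fit a whole-number convention, which the SPM may set. The SPM was not available. This also stands, but the protocol does not state the convention, and under it the 5.1 overlap widens.

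Third, silence in 6.3.3 could mean that no adjustment is needed. That is strained at the lower end. Read so, a fall to 35 calls for a reduction, a fall to 30.5 for nothing, and a fall to 30 for a stop.

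Some stronger readings are tempting but unsupported. A reader might infer that some subjects have no assigned dose. In fact every eligible subject has a starting dose, and a subject in a 6.3.3 gap is already on one and lacks only a renal-adjustment instruction. A reader might infer that the on-study reduction or stop changes with the section consulted. Only 6.3.3 gives on-study renal rules, and its stop limit agrees with the eligibility floor. Finally, 2 of 10 mL/min might be read as 20% of subjects. It is a share of the band's width, and no count of subjects follows from the documents.

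**Conclusion.** The point holds in a limited form. With the 5.1 signs as extracted, the dosing rules do not fit together whether clearance is kept with decimals or rounded. A recorded 40 has two starting doses, which also determine whether the subject has two reduction steps or none. The inclusion of 30 in 5.1 is an inconsistency of wording with no effect on who enters. The gaps in 6.3.3 are real only if decimals are kept.

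Few subjects are likely to be affected in a trial of 27 to 30. The issue deserves correction because it concerns dose and safety and is easy to remove. The conclusion rests on the 5.1 signs being as extracted and, for the gaps, on no whole-number rule being set in the SPM. If 5.1 matches the Schema and clearance is recorded in whole numbers, all that remains is to state that convention in the protocol.

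**What to change.** 1. Check the signs in the two starting-dose bands of Section 5.1 against the source PDF.
2. Reconcile criterion 11 (Synopsis and Section 3.1), the Schema footnote, Section 5.1 and Section 6.3.3 to one set of contiguous, non-overlapping CrCl bands, and repeat it identically in each place.
3. State in the protocol whether CrCl is used with decimals or rounded, and how, and make the SPM agree.

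Which dose or action applies at each boundary is for the sponsor's clinicians to decide; this review takes no view. The cost is a wording amendment, with no change to sample size, assessments or analysis.

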## 5.2 Concomitant Medications

#### 5.2.1 Allowed Concomitant Medications

All treatments that the investigator considers necessary for a subject's welfare may be administered at the discretion of the investigator in keeping with the community standards of medical care unless as otherwise indicated below.

## 5.2.1.1 Anticoagulant Therapy

Subjects who are taking warfarin may participate in this trial; however, it is recommended that international normalized ratio (INR) be monitored carefully at least once per week for the first month, then monthly if the INR is stable. Subcutaneous heparin and low molecular weight heparin are permitted.

# 5.2.1.2 Anti-emetics/Anti-Diarrheals

If a patient develops nausea, vomiting and/or diarrhea, these symptoms should be reported as AEs and should be treated per institutional guidelines.

Version Date: 15MAY2019 Confidential Page 29 of 60

## 5.2.1.3 Palliative radiotherapy

Palliative radiotherapy may be used for the treatment of pain at the site of bony metastases that were present at baseline, provided the site investigator does not feel that these are indicative of clinical disease progression during the study period. Study treatment should be discontinued for a minimum of 3 days before a patient undergoes therapeutic palliative radiation treatment. Study treatment should be restarted within 4 weeks as long as any bone marrow toxicity has recovered.

# 5.2.1.4 Contraception

# Olaparib is regarded as a compound with medium/high fetal risk.

Women of childbearing potential and their partners, who are sexually active, must agree to the use of TWO highly effective forms of contraception in combination [as listed below], throughout the period of taking study treatment and for at least 90 days after last dose of study drug(s), or they must totally/truly abstain from any form of sexual intercourse (see below).

Male subjects and their partners, who are sexually active and of childbearing potential, must agree to the use of TWO highly effective forms of contraception in combination [as listed below], throughout the period of taking study treatment and for 90 days after last dose of study drug(s) due to the unknown effects of the study drug on the sperm, or they must totally/truly abstain from any form of sexual intercourse (see below). Male subjects should not donate sperm throughout the period of taking study treatment and for 90 days following the last dose of study drug(s).

# Acceptable non-hormonal birth control methods:

- Total sexual abstinence ie, refrain from any form of sexual intercourse in line with the patients' usual and/or preferred lifestyle. Periodic abstinence (eg, calendar ovulation, symptothermal, post-ovulation methods) and withdrawal are not acceptable methods of contraception.
- Vasectomised sexual partner PLUS male condom. With participant assurance that partner received post-vasectomy confirmation of azoospermia.
- Tubal occlusion PLUS male condom
- Intrauterine Device PLUS male condom. Provided coils are copper-banded.

## Acceptable hormonal methods:

- Etonogestrel implants (eg, Implanon®, Norplant®) PLUS male condom
- Normal and low dose combined oral pills PLUS male condom
- Hormonal shot or injection (eg, Depo-Provera) PLUS male condom
- Intrauterine system device (eg, levonorgestrel-releasing intrauterine system Mirena®) PLUS male condom

## **5.2.2** Prohibited Concomitant Medications

The use of any natural/herbal products or other traditional remedies should be discouraged, but use of these products, as well as use of all vitamins, nutritional supplements, and all other concomitant medications must be recorded in the case report form (CRF).

Version Date: 15MAY2019 Confidential Page 30 of 60

## 5.2.2.1 Medications that may NOT be administered

No other anti-cancer therapy (chemotherapy, immunotherapy, hormonal therapy (Hormone replacement therapy (HRT) is acceptable), radiotherapy, biological therapy or other novel agent) is to be permitted while the patient is receiving study medication.

Live virus and live bacterial vaccines should not be administered while the patient is receiving study medication and during the 30 day follow up period. An increased risk of infection by the administration of live virus and bacterial vaccines has been observed with conventional chemotherapy drugs and the effects with olaparib are unknown.

#### **5.2.2.2** Restricted concomitant medications

Subjects must not be taking strong or moderate CYP3A inhibitors or strong or moderate CYP3A inducers at the time of study enrollment. Subjects for whom these medications are being considered after subjects have already been enrolled on study should follow the guidance below:

# Strong or Moderate CYP3A inhibitors

Known strong CYP3A inhibitors (e.g., itraconazole, telithromycin, clarithromycin, boosted protease inhibitors, indinavir, saquinavir, nelfinavir, boceprevir, telaprevir) or moderate CYP3A inhibitors (ciprofloxacin, erythromycin, diltiazem, fluconazole, verapamil) should not be taken with olaparib.

If there is no suitable alternative concomitant medication then the dose of olaparib should be reduced for the period of concomitant administration. The dose reduction of olaparib should be recorded in the eCRF with the reason documented as concomitant CYP3A inhibitor use.

- Strong CYP3A inhibitors reduce the dose of olaparib to 100 mg bid for the duration of concomitant therapy with the strong inhibitor and for 5 half-lives afterwards.
- Moderate CYP3A inhibitors reduce the dose of olaparib to 150 mg bid for the duration of concomitant therapy with the moderate inhibitor and for 3 half-lives afterwards.
- After the washout of the inhibitor is complete, the olaparib dose can be re-escalated.

## Strong or Moderate CYP3A inducers

Strong (e.g., phenobarbital, phenytoin, rifampicin, rifabutin, rifapentine, carbamazepine, nevirapine, enzalutamide and St John's Wort) and moderate CYP3A inducers (eg. bosentan, efavirenz, modafinil) of CYP3A should not be taken with olaparib.

If the use of any strong or moderate CYP3A inducers are considered necessary for the patient's safety and welfare this could diminish the clinical efficacy of olaparib.

If a patient requires use of a strong or moderate CYP3A inducer or inhibitor then they must be monitored carefully for any change in efficacy of olaparib.

## *P-gp inhibitors*

It is possible that co-administration of P-gp inhibitors (eg amiodarone, azithromycin) may increase exposure to olaparib. Caution should therefore be observed.

Version Date: 15MAY2019 Confidential Page 31 of 60

## Effect of olaparib on other drugs

Based on limited *in vitro* data, olaparib may increase the exposure to substrates of CYP3A4, P-gp, OATP1B1, OCT1, OCT2, OAT3, MATE1 and MATE2K. Based on limited *in vitro* data, olaparib may reduce the exposure to substrates of CYP3A4, CYP1A2, 2B6, 2C9, 2C19 and P-gp.

The efficacy of hormonal contraceptives may be reduced if co administered with olaparib. Caution should therefore be observed if substrates of these isoenzymes or transporter proteins are co-administered.

## Examples of substrates include:

- CYP3A4 hormonal contraceptive, simvastatin, cisapride, cyclosporine, ergot alkaloids, fentanyl, pimozide, sirolimus, tacrolimus and quetiapine
- CYP1A2 duloxetine, melatonin
- CYP2B6 bupropion, efavirenz
- CYP2C9 warfarin
- CYP2C19 lansoprazole, omeprazole, S-mephenytoin
- P-gp simvastatin, pravastatin, digoxin, dabigatran, colchicine
- OATP1B1 bosentan, glibenclamide, repaglinide, statins and valsartan
- OCT1, MATE1, MATE2K metformin
- OCT2 serum creatinine
- OAT3 -furosemide, methotrexate

# 5.2.2.3 Administration of other anti-cancer agents

Subjects must not receive any other concurrent anti-cancer therapy, including investigational agents, while on study treatment. Subjects may continue the use of bisphosphonates or denosumab for bone disease.

# 6. TOXICITIES AND DOSE DELAYS/DOSE MODIFICATIONS

The NCI Common Terminology Criteria for Adverse Events (CTCAE) v4.03 will be used to grade adverse events.

Subjects enrolled in this study will be evaluated clinically and with standard laboratory tests before and at regular intervals during their participation in this study as specified in Study Calendar & Evaluations.

Subjects will be evaluated for adverse events (all grades), serious adverse events, and adverse events requiring study drug interruption or discontinuation as specified in Study Calendar & Evaluations.

# **6.1** Dose Delays/Dose Modifications

For guidance on dose reductions when concomitant strong or moderate CYP3A inhibitors or inducers cannot be avoided see section 5.2.2.

Any toxicity observed during the course of the study could be managed by interruption of the dose of study treatment or dose reductions. Repeat dose interruptions are allowed as required, for a maximum of 4 weeks on each occasion. If the interruption is > 4 weeks, the sponsor-

Version Date: 15MAY2019 Confidential Page 32 of 60

investigator should be informed. Study treatment can be dose reduced to 250 mg twice daily as a first step and to 200 mg twice daily as a second step. If the reduced dose of 200 mg twice daily is not tolerable, no further dose reduction is allowed and study treatment should be discontinued. There will be no dose reductions for subjects (with moderate renal insufficiency) starting at a dose of 200 mg twice daily.

